#### Other Definitions:

Treatment completers are those subjects that are compliant with IMP at least 85% of dosing days and fulfill at least one of the following criteria:

- Subjects that did not discontinue from the trial prior to end of study visit at Day 99 ± 4 days (Visit 12).
- Subjects that complete the Treatment Period (T+M) starting from Study Day 1 through the protocol defined end of study visit at Day 99 ± 4 days (Visit 12).
- Subjects that enroll in the open label extension study.

### 6.3. Multiplicity Strategy and Testing Hierarchy

Multiplicity issues in the statistical inference in this study arise from two sources: (a) multiple treatment comparisons, and (b) multiple endpoints.

This document is confidential.

## Statistical Analysis Plan

Sponsor: Zogenix International Limited; Protocol No.: ZX008 Study 2 (ZX008-1501 and ZX008-1502)

---

The efficacy analyses will employ a serial gatekeeper strategy to maintain the Type 1 error rate at  $\alpha=0.05$  across the family of analyses that support the primary and key secondary objectives.

All statistical analyses will be performed and results tabulated with test statistics, p-values, and/or 95% confidence intervals.

Formal statistical testing will be performed for 1 primary endpoint and 2 secondary endpoints, for the comparison of ZX008 0.8 mg/kg with Placebo, and between ZX008 0.2 mg/kg with Placebo. Hence there are 6 formal hypothesis tests: 1 primary hypothesis test and 5 secondary hypothesis tests. To preserve the overall Type 1 error rate at  $\alpha=0.05$ , these tests will proceed as follows:

Step 1: The primary efficacy endpoint (mean convulsive seizure frequency per 28 days) will be formally tested first between the 0.8 mg/kg and Placebo group. If the comparison is statistically significant at the  $\alpha=0.05$  (2-sided) level, hypothesis testing will proceed to Step 2. Otherwise formal testing of the other hypotheses stops.

Step 2: The secondary efficacy endpoint, the proportion of subjects who achieve a  $\geq 50\%$  reduction from baseline in convulsive seizure frequency, will be compared between the 0.8 mg/kg and Placebo group. If the comparison is statistically significant at the  $\alpha=0.05$  (2-sided) level, hypothesis testing will proceed to Step 3. Otherwise formal testing of the other hypotheses stops.

Step 3: The endpoint, the longest convulsive seizure-free interval will be compared between 0.8 mg/kg and Placebo. If the comparison is statistically significant at the  $\alpha=0.05$  (2-sided) level, hypothesis testing will proceed to Step 4. Otherwise formal testing stops.

Step 4: The mean convulsive seizure frequency per 28 days will be formally tested first between the 0.2 mg/kg and Placebo group. If the comparison is statistically significant at the  $\alpha=0.05$  (2-sided) level, hypothesis testing will proceed to Step 5. Otherwise formal testing of the other hypotheses stops.

Step 5: The secondary efficacy endpoint, the proportion of subjects who achieve a  $\geq 50\%$  reduction from baseline in convulsive seizure frequency, will be compared between the 0.2 mg/kg and Placebo group. If the comparison is statistically significant at the  $\alpha=0.05$  (2-sided) level, hypothesis testing will proceed to Step 6. Otherwise formal testing of the other hypotheses stops.

Step 6: The endpoint, the longest convulsive seizure-free interval will be compared between 0.2 mg/kg and Placebo using a significance level of  $\alpha=0.05$  (2-sided).

### 6.4. Missing Data

Imputation for missing data is used in the sensitivity efficacy analyses.

#### Seizure Diaries:

Seizures are recorded in the Daily Seizure Diary (DSD). The End of Day Diary (EDD) provides Yes/No confirmation that seizures were experienced for a specific date or that the date was seizure free. The DSD was programmed to allow for up to 7 days of retrospective entry for daily seizures and to allow entry for EDD by 11:59 pm each day to confirm (Y/N) each day whether the day was seizure-free. Changes outside these parameters would therefore need to be made via the Data Clarification Request (DCR) process. Additionally, through a pre-specified process DCRs were used to categorize new seizures that

This document is confidential.

emerged during the treatment period. Specifically, new seizures were entered into the DSD as “Other” and after review of the seizure description by the Epilepsy Study Consortium, “Other” was updated to the appropriate clinical term via DCR.

DCR data were processed prior to applying the missing data rules described below:

- If no seizures are entered in the DSD and the EDD confirms seizure freedom, the number of seizures for that date is zero.
- If seizures are entered in the DSD and the EDD states seizure freedom, the seizures recorded for that date supersede the EDD stating seizure freedom.
- If no seizures are entered in the DSD and there is no response in the EDD, that day will be considered to have missing diary data.
- If no seizures are entered in the DSD and there is a Yes response in the EDD, that day will be considered to have missing diary data.

Based on analyses of the blinded, pre-lock database for Study 1, seizures clusters that were entered into the DSD without a number of seizures in the cluster had a value of 3 was imputed for the seizure count.

#### **Missing Data Due to Dropouts:**

The issue of missing data has gained much attention subsequent to the National Academy of Science Report on the Treatment and Handling of Missing Data (NAS Report, 2010). Within the context of the studies, missing data arise from two sources: intermittent missing assessments (such as missing diary data), and as a result of dropouts prior to the end of the titration + maintenance periods.

In Study 1, only 2 (out of the 119) subjects had more than 7 days of missing diary data while on treatment (before dropout). The rates of dropout in the pivotal trials was 7.56% (9/119) in Study 1. Dropouts that are related to treatment response leave the possibility that the analysis of efficacy endpoints, which relies on assumptions of data being missing at random (MAR), may be violated. It is possible, though, that data may be missing not at random (MNAR). Differential dropouts leading to missing assessments may thus affect the inference on the primary endpoint.

The primary analysis method, in so far as it uses the convulsive seizure frequency averaged over the entire treatment period, in effect, assumes that a dropout would have followed the mean profile experienced up to that point in time when the subject dropped out from the study. Alternative, explicit, ways of addressing the issue of missing seizure data due to dropouts may be considered. (Kenward 2015) Two methods were chosen for minimal impact on variability of estimates as well as their simplicity.

It is assumed that the **planned duration** of T+M for Study 1 and Study 2 subjects is 14 weeks (98 days).

*S1: Worst value substituted:* In this analysis, for a subject who drops out of treatment, if the convulsive seizure frequency during T+M is lower than the baseline value, the baseline value will be substituted for the subject from the point of withdrawal to the end of the planned duration of T+M. However, if it is higher than the baseline, there will be no substitution. The CSF for the planned duration of T+M will then be computed as a weighted mean of the value before dropout, and the imputed value after dropout. The weights will be the proportion of planned duration of T+M before and after dropout. The statistical analysis (parametric ANCOVA with  $\log CSF_{T+M}$  as response and  $\log CSF_B$  as covariate, along with age group, treatment (2 factors: placebo, ZX008)) will then be performed on the resulting dataset. Treatment comparisons will be based on the least squares means and standard errors obtained from the ANCOVA.

This document is confidential.

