## Primary Analysis

### T+M Period:

The primary analysis will compare the ZX008 0.8 mg/kg/day group to the placebo group using a two-sided test at the  $\alpha=0.05$  level of significance.

The primary endpoint ( $CSF_{T+M}$ ) will be analyzed using an analysis of covariance (ANCOVA) model with treatment group (three levels) and age group (< 6 years,  $\geq 6$  years) as factors, log baseline  $CSF_B$  as a covariate and log  $CSF_{T+M}$  as response. Treatment group mean differences from placebo will be estimated via least squares means from the analysis model along with 95% confidence intervals and associated 2-sided p-values. Estimated treatment differences and CI endpoints will be exponentiated for presentation.

The null hypothesis

$$H_0: \mu_{Z0.8} - \mu_P = 0,$$

will be tested against the alternative

$$H_A: \mu_{Z0.8} - \mu_P \neq 0,$$

where  $\mu_{Z0.8}$  and  $\mu_P$  represent the ZX008 0.8 mg/kg and Placebo group means (on the log scale), respectively.

Rejection of the null hypothesis in favor of the alternative, in the presence of a statistically significantly smaller mean convulsive seizure frequency for the treatment group compared to the placebo group, (two-sided p-value < 0.05) will be regarded as evidence of a treatment benefit in favor of the 0.8 mg/kg group.

Sample SAS code for the ANCOVA described above is as follows:

```
proc glm data=temp;
  class agegrp trtp;
  model csftm = bcsf agegrp trtp / SS3;
  lsmeans trtp / pdiff stderr;
```

where trtp = randomized treatment group (with codes 1, 2, 3 indicating placebo, 0.2 mg, and 0.8 mg groups).

```
bcsf = log( CSFB ),
csftm = log( CSFT+M + 1 ),
agegrp = age group.
```

Additional statements may be used to obtain estimates and associated 95% confidence intervals. Endpoints of the CIs may be exponentiated to obtain CI on the original scale. Fitted values and residuals will be plotted to check model assumptions.

Since the ANCOVA used in the primary analysis relies on assumptions of normality, the primary endpoint will also be analyzed using a nonparametric method that does not require as stringent assumptions. A nonparametric ANCOVA will be used to analyze the data, with ranks of the baseline  $CSF_B$  as a covariate and ranks of  $CSF_{T+M}$  as response, and the results will be used to assess the primary objective. If normality assumptions are not met, the results of the nonparametric test will be used to assess the primary objective.

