**Statistical Analysis Plan**

Sponsor: Zogenix International Limited; Protocol No.: ZX008 Study 2 (ZX008-1501 and ZX008-1502)

Table	14.2.15.7	Convulsive seizure frequency per 28 days During Double-blind Treatment: Parametric Analysis, by Concomitant Clobazam Use - mITT Population
Table	14.2.15.7a	Convulsive seizure frequency per 28 days During Double-blind Treatment: Parametric Analysis, by Concomitant Clobazam Use (Japan) - mITT Population
Table	14.2.15.9	Convulsive seizure frequency per 28 days During Double-blind Treatment: Parametric Analysis, by SCN1A Mutation Positive/Negative - mITT Population
Table	14.2.15.9a	Convulsive seizure frequency per 28 days During Double-blind Treatment: Parametric Analysis, by SCN1A Mutation Positive/Negative (Japan) - mITT Population
Figure	14.2.15.10	Scatterplot of Percentage Change in CSF per 28 days vs. Actual Dose Administered During Double-blind Treatment (mg/kg/day) - mITT Population
Figure	14.2.15.10a	Scatterplot of Percentage Change in CSF per 28 days vs. Actual Dose Administered During Double-blind Treatment (mg/kg/day) (Japan) - mITT Population
Figure	14.2.15.10b	Scatterplot of Percentage Change in CSF per 28 days vs. Actual Dose Administered During Double-blind Treatment (mg/kg/day) (Non-Japan) - mITT Population
Figure	14.2.15.11	Scatterplot of Percent Change in CSF per 28 days vs. Actual dose (mg/day) - mITT Population
Figure	14.2.15.11a	Scatterplot of Percent Change in CSF per 28 days vs. Actual dose (mg/day) (Japan) - mITT Population
Figure	14.2.15.11b	Scatterplot of Percent Change in CSF per 28 days vs. Actual dose (mg/day) (Non-Japan) - mITT Population
Table	14.2.15.12	Convulsive seizure frequency per 28 days – Sensitivity Analysis S1 Worst value substituted for dropouts - mITT Population
Table	14.2.15.12a	Convulsive seizure frequency per 28 days – Sensitivity Analysis S1 Worst value substituted for dropouts (Non-Japan) - mITT Population
Table	14.2.15.13	Convulsive seizure frequency per 28 days – Sensitivity Analysis S2 Differential imputation method for dropouts - mITT Population
Table	14.2.15.13a	Convulsive seizure frequency per 28 days – Sensitivity Analysis S2 Differential imputation method for dropouts (Non-Japan) - mITT Population
Table	14.2.15.14	Convulsive Seizure Frequency per 28 Days (Intermediate Missing Day and Post-Discontinuation Imputation): Parametric Analysis - mITT Population

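### Study 2 sensitivity analysis S1 is specified with a two-level treatment term (placebo, ZX008), so as written it gives no 0.8 mg/kg/day versus placebo estimate to set against the primary result

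*SAP*

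**What the plan says.** All references are to the Study 2 SAP of May 2020.

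- **Purpose of S1 (section 6.4, Missing Data Due to Dropouts).** Dropout related to response may bias inference on the primary endpoint, and two simple methods, S1 and S2, are chosen to examine this.
- **Imputation in S1.** For a dropout whose on-treatment frequency is below baseline, "the baseline value will be substituted for the subject from the point of withdrawal to the end of the planned duration of T+M". The two parts are combined as a weighted mean over 98 days.
- **Model in S1.** A parametric ANCOVA of log CSF in T+M on log baseline CSF, "along with age group, treatment (2 factors: placebo, ZX008)) will then be performed on the resulting dataset". Comparisons come from that model's least squares means. No dose is named.
- **Primary model (section 8.1, T+M Period).** An "analysis of covariance (ANCOVA) model with treatment group (three levels) and age group", with treatment coded "with codes 1, 2, 3 indicating placebo, 0.2 mg, and 0.8 mg groups". The contrast is fixed: "The primary analysis will compare the ZX008 0.8 mg/kg/day group to the placebo group using a two-sided test". The prose says log CSF for the response, and the sample code defines it as "csftm = log( CSFT+M + 1)".
- **Other two-level wording.** The responder model (section 8.2.1) and the status epilepticus model (section 8.2.2) also describe treatment as active or placebo. The first then reports each dose against placebo separately. The second names 0.8 mg/kg/day and adds an analogous model for 0.2 mg/kg/day.
- **Planned output (section 15).** Table 14.2.15.12 is the S1 table. Its title mentions neither a dose nor pooling.

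**The concern.** A sensitivity analysis for missing data should change the handling of missing data and nothing else. S1 also changes the treatment term. With two levels there is a single contrast, any ZX008 against placebo. That is neither Step 1 (0.8 mg/kg/day) nor Step 4 (0.2 mg/kg/day) of the hierarchy in section 6.3.

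If S1 is programmed as written, a smaller effect than in the primary analysis could reflect dilution by the lower dose, the imputation, or both, and the output would not separate them. The error can also run the other way: an effect confined to 0.2 mg/kg/day could make S1 look supportive of a 0.8 mg/kg/day result that it had not examined.

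**Working it through.** **Figures stated in the plan.** Section 2.5 gives 40 per arm for 90% power, a 40-point difference, SD 55% and two-sided alpha 0.05.

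- n = 2 × (1.960 + 1.282)² × 55² / 40² = 39.7, so 40 per arm.
- Power at 40 per arm is 90.2% (normal approximation; 89.5% with the noncentral t).
- Study 1 dropout: 9/119 = 7.56%, as section 6.4 states.

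These reproduce. They do not bear on the S1 wording but supply the arm sizes and SD used below.

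**What a two-level term estimates.** With equal arms and balanced covariates, the pooled active mean on the log scale is the average of the two dose means. The pooled ratio to placebo is therefore exp[(ln r₀.₈ + ln r₀.₂)/2]. This ignores the +1 offset. The ratios are assumptions, because the documents give no dose-specific effects.

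| r for 0.8 | r for 0.2 | Pooled ratio | Reduction from pooled S1 | Reduction for 0.8 |
|---|---|---|---|---|
| 0.4 | 0.7 | √0.28 = 0.529 | 47% | 60% |
| 0.4 | 1.0 | √0.40 = 0.632 | 37% | 60% |

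The gap is 13 to 23 percentage points before anyone drops out.

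**The same on the sample-size scale.** Take a 40-point effect for 0.8 mg/kg/day, and for 0.2 mg/kg/day a fraction f of it (assumed). The pooled contrast is 40(1 + f)/2. With 80 active and 40 placebo subjects its standard error is 55 × √(1/80 + 1/40) = 10.65.

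| f | Pooled contrast (points) | Power |
|---|---|---|
| 0 | 20 | 46.7% |
| 0.25 | 25 | 65.1% |
| 0.5 | 30 | 80.4% |
| 0.75 | 35 | 90.8% |
| 1 | 40 | 96.4% |

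The comparison of 0.8 mg/kg/day with placebo at 40:40 has 90.2%. If instead 0.8 mg/kg/day had no effect and 0.2 mg/kg/day had 40 points, the pooled contrast would again be 20 points and would reject 46.7% of the time.

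**Check with the +1 kept.** A simulation without dropouts used log(CSF + 1), 40 per arm, a median baseline of 20 per 28 days and 600 runs (all assumed). Rate multipliers were 0.9 for placebo, 0.6 for 0.2 mg/kg/day and 0.4 for 0.8 mg/kg/day. The three-level model gave 0.514 for 0.8 against placebo; the two-level model gave 0.604. The offset narrows the gap but does not remove it.

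**Zero counts.** Under the section 8.1 code, a subject with no seizures has log(0 + 1) = 0, which is defined. A seizure-free dropout is not at zero after S1 anyway: with an assumed baseline of 20 and withdrawal on day 49 of 98, S1 gives (1 − 49/98) × 20 = 10.0.

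**The case against.** The best reply is that the two-level wording is shorthand for pairwise models. The SAP nowhere says that the doses are pooled. The responder and status epilepticus sections use the same kind of label for dose-specific models, S1 speaks of comparisons in the plural, and section 6.1 presents Study 2 summaries in three groups. This stands to the extent that pooling is the literal reading, not the only one. It does not clear the text, because the two parallel sections each say that the doses are taken separately and S1 does not. Even a pairwise S1 would not be the primary model. Dropping an arm changes the fitted baseline and age coefficients, and residual degrees of freedom go from 120 − 5 = 115 to 80 − 4 = 76. That is minor, but avoidable.

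A second reply is that little depends on S1. It lies outside the hierarchy in section 6.3, section 8.1 rests efficacy on the primary log-scale analysis, Study 1 dropout was 7.56%, and the S2 text contains no two-level term. This stands and limits the severity.

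Two stronger readings are tempting and are not supported:

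- A reader might infer that S1 takes the log of zero and so loses the seizure-free subjects, because its text omits the +1. Its prose for the response is the same as the primary model's, and the section 8.1 code defines that response with the offset. Nothing in S1 removes it.
- A reader might take the index title "Sensitivity Analysis S2 Differential imputation method for dropouts" (Table 14.2.15.13) as contradicting the S2 text. S2 does impute differently by arm, so the label fits. Since Table 14.2.15.14 carries the name used in the text, a cross-reference is needed, but that is editorial.

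**Conclusion.** The treatment term in S1 is inconsistent with the model that S1 is meant to stress. Read literally, S1 yields no estimate for 0.8 mg/kg/day or for 0.2 mg/kg/day against placebo, and a departure from the primary result could not be attributed to dropout. Under the assumed ratios the displacement is 13 to 23 percentage points with no dropouts. It depends entirely on the literal reading and on how far the doses differ, and it vanishes if they have equal effects. It would be too strong to say that S1 cannot test the primary comparison; as written, it does not commit to doing so. This should be fixed before unblinding. It is not critical, because the primary analysis and the testing hierarchy are untouched.

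**What to change.** In section 6.4, replace the S1 model with that of section 8.1: treatment at three levels, age group, log baseline CSF as covariate, and log(CSF in T+M + 1) as response. The +1 is restated for clarity only. State that the least squares mean contrasts 0.8 mg/kg/day versus placebo and 0.2 mg/kg/day versus placebo are reported separately in Table 14.2.15.12.

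As a separate editorial item, say which of Tables 14.2.15.13 to 14.2.15.15 present S2 as defined in the text.

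The cost is wording. The imputation rule and the imputed dataset do not change.

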**Statistical Analysis Plan**

Sponsor: Zogenix International Limited; Protocol No.: ZX008 Study 2 (ZX008-1501 and ZX008-1502)

**S2: Intermediate Missing Day and Post-Discontinuation Imputation:** Intermediate missing days should be imputed as the worse observed outcome for that patient if the patient was assigned to an active arm or zero seizures if the patient was assigned to placebo.

For patients who discontinued the study, the day of discontinuation should be imputed as the worse observed outcome if assigned to ZX008 and as zero counts if the patient was assigned to placebo. The remaining days should be imputed using the baseline seizure counts for all arms.

For cluster seizures that were reported as uncountable, the assigned number of seizures in the cluster is assigned as the worst cluster value for each individual subject in the active arm, and assigned as the mean baseline seizure count if the subject was assigned to placebo.

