**Statistical Analysis Plan**

Sponsor: Zogenix International Limited; Protocol No.: ZX008 Study 2 (ZX008-1501 and ZX008-1502)

---

- Impute the number of seizures in an uncountable cluster was added. Such an imputation is necessary to make it possible to calculate seizure frequency. For cluster seizures that were reported as uncountable, the assigned number of seizures in the cluster is assigned as 3.

This document cannot be used to support any marketing authorization application and any extensions or variations thereof.

PUBLIC COPY

This document is confidential.

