Table	14.2.15.15	Convulsive Seizure Frequency per 28 Days (Intermediate Missing Day, Post-Discontinuation, and Cluster Imputation): Parametric Analysis - mITT Population
	14.3	Safety
	14.3.1	Summary of adverse events
Table	14.3.1.1	Overview of Number of Subjects with TEAE, DB Treatment Period – Safety Population
Table	14.3.1.1a	Overview of Number of Subjects with TEAE, DB Treatment Period (Japan) – Safety Population
Table	14.3.1.1b	Overview of Number of Subjects with TEAE, DB Treatment Period (Non-Japan) – Safety Population
Table	14.3.1.2	Treatment-Emergent Adverse Events by MedDRA System Organ Class and Preferred Term – Safety Population
Table	14.3.1.2a	Treatment-Emergent Adverse Events by MedDRA System Organ Class and Preferred Term (Japan) – Safety Population

This document is confidential.

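### Sensitivity analysis S2 gives an uncountable placebo cluster a baseline mean with no unit instead of a cluster size, so its direction depends on the reading and it cannot test the main-rule value of 3

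*SAP*

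**What the plan says.** All references are to the Study 2 SAP.

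- **Main rule.** Section 6.4 (Seizure Diaries) says that "seizures clusters that were entered into the DSD without a number of seizures in the cluster had a value of 3 was imputed". Section 12 repeats it: "For cluster seizures that were reported as uncountable, the assigned number of seizures in the cluster is assigned as 3". Neither distinguishes between arms.
- **S2, active arms** (Section 6.4): "the assigned number of seizures in the cluster is assigned as the worst cluster value for each individual subject in the active arm".
- **S2, placebo** (same sentence): "assigned as the mean baseline seizure count if the subject was assigned to placebo".
- **S2, other rules.** Isolated missing days take the worst observed outcome on active drug and "zero seizures if the patient was assigned to placebo". The day of discontinuation is split in the same way. After that, "The remaining days should be imputed using the baseline seizure counts for all arms".
- **Output.** Section 15 lists Table 14.2.15.15 with "Intermediate Missing Day, Post-Discontinuation, and Cluster Imputation" in its title. Table 14.2.15.14 has the same title without the cluster part. Table 14.2.15.13 carries the S2 label, but its title mentions dropouts only.

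**The concern.** The two halves of the S2 cluster rule are on different scales. The active half asks how large this subject's clusters get. The placebo half asks for an average of baseline seizures, without saying whether that is per day, per 28 days or over the 42-day baseline, and without saying whether it belongs to the subject or the arm. Two programmers could follow the sentence faithfully and obtain different data sets.

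The active half has gaps of its own. A subject with no counted cluster has no worst one, and no fallback is given. If a subject's largest counted cluster is 2, S2 is milder than the main rule for that subject.

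Table 14.2.15.15 is the only listed output whose title names cluster imputation, so it is the plan's only visible check on the choice of 3. With an undefined placebo input it cannot show whether the result is robust to that choice, and the unit could be settled after the data are seen.

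**Working it through.** The plan gives no numerical result for this rule, so there is no figure of its own to reproduce.

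**Inputs.** Planned T+M is 98 days (Section 6.4). Baseline is 42 days (Section 6.2). CSF is per 28 days and the ANCOVA response is log(CSF + 1) (Section 8.1). The main-rule cluster value is 3. Baseline frequencies (CSF_B) of 10 and 50 are the plan's category limits (Section 8.1); 20 is an added intermediate value.

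**Value imputed for one placebo cluster, v**
- per day: CSF_B / 28
- per 28 days: CSF_B
- per 42-day baseline: 42 × CSF_B / 28 = 1.5 × CSF_B

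**Where v passes 3.** Per 28 days: CSF_B > 3. Per 42 days: CSF_B > 3 / 1.5 = 2. Per day: CSF_B > 3 × 28 = 84. The daily value is below 2 when CSF_B < 56, which covers the whole of the plan's two lower baseline categories. It is below 1 when CSF_B < 28, so a recorded cluster would then count as less than one seizure.

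**Effect on one subject.** One cluster adds 28v / 98 to CSF over T+M. With v = 3 that is 0.86.

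| CSF_B | added, per day | added, per 28 days | added, per 42 days |
|---|---|---|---|
| 10 | 0.10 | 2.86 | 4.29 |
| 20 | 0.20 | 5.71 | 8.57 |
| 50 | 0.51 | 14.29 | 21.43 |

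Assume that the subject's other T+M seizures run at 0.87 × CSF_B. This borrows the 13% placebo reduction of the external trial cited in Section 2.5, for illustration only. The ratio of (CSF + 1) to its value with v = 3 is then:

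| CSF_B | per day | per 28 days | per 42 days |
|---|---|---|---|
| 10 | 0.93 | 1.19 | 1.32 |
| 20 | 0.97 | 1.25 | 1.40 |
| 50 | 0.99 | 1.30 | 1.45 |

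For example, at CSF_B = 10 per 28 days: (8.7 + 2.86 + 1) / (8.7 + 0.86 + 1) = 1.19.

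**A subject with several clusters.** Take 40 seizures per 28 days (140 over T+M) and 5 uncountable clusters.
- v = 3: 28 × (140 + 15) / 98 = 44.3
- daily: 28 × (140 + 7.14) / 98 = 42.0
- 28-day: 28 × (140 + 200) / 98 = 97.1

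Over CSF 20 to 80 and 2 to 10 clusters, the 28-day reading gives 1.45 (110/76) to 3.5 (1080/310) times the CSF obtained with 3. The daily reading gives 0.77 to 1.0 times.

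**Effect on the arm.** If a share s of placebo subjects has one such cluster, the placebo geometric mean of (CSF + 1) is multiplied by exp(s × ln ratio). With s = 10% and CSF_B from 10 to 50, the change is +1.7% to +2.6% per 28 days, +2.9% to +3.8% per 42 days, and -0.7% to -0.1% per day. With s from 5% to 20%, the 28-day range is +0.9% to +5.3% and the daily range is -1.5% to -0.04%. The share is an assumption; the plan does not report how many clusters were uncountable.

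**The case against.** The tempting stronger reading is that S2 uses the plan's 28-day scale, so that it inflates placebo seizures and favours ZX008. The text does not support this. Section 8.1 calls the 28-day quantity a frequency, and the mean it forms from it is an arm average; S2 speaks of a count. The sentence just before the cluster rule fills baseline counts into days, so a daily reading is at least as natural. On that reading the placebo value is below 3 for any CSF_B under 84, which leans against ZX008 like the other differential rules in S2. No bias in a known direction is shown, and the 2.2-fold gap (97.1 against 44.3) belongs to one hypothetical subject.

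It is also fair to say that a sensitivity analysis may depart from 3 without contradicting the main rule, and that the arm-level shifts above are small. The plan itself never calls S2 conservative; that is inferred from its rules for missing days and for the day of discontinuation.

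These points remove any claim about direction, but not the defect. The daily reading replaces a value that is too large with one that is usually too small to be a cluster. The author may have meant the mean number of seizures per baseline cluster, but the sentence does not say so, and that value too could exceed 3. The gaps in the active rule do not depend on any of these readings.

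**Conclusion.** The point holds as a specification error in one sensitivity analysis. The placebo value is not defined on a cluster scale. On a 28- or 42-day reading it inflates placebo counts relative to 3 for almost any baseline; on a daily reading it usually deflates them. The active rule is undefined without a counted cluster and can be milder than the main rule. As written, Table 14.2.15.15 therefore cannot test the value 3.

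The direction and size of the net effect cannot be settled from the plan. They depend on the unit, on the active subjects' worst clusters and on the number of uncountable clusters, none of which the plan gives. The percentages above rest on an assumed share of subjects, one cluster each, and a borrowed placebo response. The primary analysis, which uses 3 in all arms, is untouched. This should be corrected, but it does not threaten the main conclusion.

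**What to change.** Rewrite the S2 cluster rule per cluster in both arms, so that S2 is never milder than the main rule:

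- **Active arms:** the larger of 3 and the subject's largest counted cluster; 3 if the subject has none.
- **Placebo:** the smaller of 3 and the subject's smallest counted cluster. If the subject has none, use a fallback fixed before unblinding, for example 2. That number is an assumption, because the plan gives no minimum cluster size.
- **Primary analysis:** keep 3 in all arms.

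If unblinding has already taken place, record which reading was programmed and present the per-cluster version as an added analysis.

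The cost is two sentences in Section 6.4 and a small program change. S2 may become more or less favourable to ZX008, depending on the reading that would have been used. Against the 28-day reading, the placebo side becomes less favourable. Against the daily reading, a fallback of 2 exceeds the present value for any CSF_B below 56, so the placebo side becomes more favourable.
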